This study will utilize a cluster-randomized trial design. Entire libraries will be randomized to either offer community members the virtual reality training or the standard educational offerings (e.g. handouts, online videos). Volunteers will be asked to complete the brief, anonymous, and validated Opioid Overdose Knowledge Scale & Opioid Overdose Attitudes Scale prior to receiving an education intervention (pretest) and then again immediately after (posttest). Neither participants nor investigators will be blinded. Library patrons who do not participate in the study will be offered current standard training materials. Regardless of the library's randomization, to either virtual reality or standard training, all patrons completing pre and post test surveys will have the opportunity to view the virtual reality training or other public health department materials.

Study duration

The new project dates of the proposed study are September 2019-August 2020. This will enable enrollment to occur throughout September at "Naloxone Handout Days" as well as at once monthly trainings offered by the department of public health at the South Philadelphia Library for local community members to walk in.

Characteristics of the Study Population

Target population

Our target population includes library patrons voluntarily attending the department of public health's "naloxone handout days" and monthly educational trainings. This enrollment strategy across free libraries and zip codes will provide ample opportunities for local city residents living in diverse settings to attend and receive valuable opioid overdose education.

Subjects enrolled by Penn Researchers

125

Subjects enrolled by Collaborating Researchers

0

Vulnerable Populations

Children Form

Pregnant women (if the study procedures may affect the condition of the pregnant woman or fetus) Form

Fetuses and/or Neonates Form

Prisoners Form

Other

None of the above populations are included in the research study

The following documents are currently attached to this item:

There are no documents attached for this item.

Subject recruitment

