
The following documents are currently attached to this item:

There are no documents attached for this item.

Deception

Does your project use deception?

No

International Research

Are you conducting research outside of the United States?

No

Analysis Plan

Descriptive statistics will be calculated for the sample by cluster. Cohorts will be evaluated, pretest, for

differences in demographic characteristics using independent sample t-test, or chi-square test of proportions when appropriate. Similarly, independent t-test will assess differences in pre-test knowledge and attitudes prior to intervention between control and experimental groups, and again with a posttest analysis. Paired t-test will assess within cohort changes in knowledge and attitudes towards recognizing signs of overdose and intervening during an observed opioid related overdose in the community settings. Sample sizes of 30-50 participants, when sampling 6-10 libraries, or clusters, with an with an average of 5 subjects in each cluster, achieves 85% to 94% power to detect a difference in OOKS scores between the group means of at least 4 points using a two sided t-test at significance level of 0.05. The standard deviation of subjects is 5. The intracluster correlation coefficient is assumed to be 0.010. Structural equation modeling will assess differences in control and treatment participants post scores while adjusting for relevant covariates including baseline knowledge and attitudes.

The following documents are currently attached to this item:

There are no documents attached for this item.

Subject Confidentiality

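### The stated 85% to 94% power does not follow from the stated inputs, whether 30-50 participants is a total (55% to 78%) or a per-arm count (85% to 97%), and the enrolment of 125 is not tied to either

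*Combined protocol and SAP*

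**What the plan says.** The power statement is in the Analysis Plan section. It gives the size as "Sample sizes of 30-50 participants, when sampling 6-10 libraries, or clusters, with an with an average of 5 subjects in each cluster" and says that this "achieves 85% to 94% power to detect a difference in OOKS scores between the group means of at least 4 points", using a two-sided t-test at the 0.05 level. The remaining inputs follow directly: "The standard deviation of subjects is 5" and "The intracluster correlation coefficient is assumed to be 0.010".

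The Design section says "Entire libraries will be randomized to either offer community members the virtual reality training or the standard educational offerings". It gives neither an allocation ratio nor a number of libraries per arm.

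Under Characteristics of the Study Population, the entry for "Subjects enrolled by Penn Researchers" is 125. The Study duration section extends enrolment beyond the September handout days to "once monthly trainings offered by the department of public health at the South Philadelphia Library". The text available does not connect 125 to the 30-50 participants, to the 6-10 libraries or to the power range, and it gives no allowance for loss.

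**The concern.** The participant and library counts agree with each other at 5 per library (6 × 5 = 30, 10 × 5 = 50), and nothing marks them as per arm. A reader will take them as the size of the whole trial. Yet 15 to 25 people per arm looks too few for 85% to 94% power at a standardised difference of 4/5 = 0.8.

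This is the only justification of sample size in the documents. If the sentence is used as the recruitment target, the trial could stop at a size that does not give the power claimed for its own 4-point difference. The number of libraries matters as much, because libraries are the randomised units, and the sentence leaves open whether 6-10 or 12-20 are needed. The 125 adds a third possible size that is not explained.

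**Working it through.** **Inputs (Analysis Plan).** Difference 4; SD 5; ICC 0.010; 5 participants per library; two-sided t-test, alpha 0.05. The allocation is not stated, so equal arms are assumed first and other splits are tried afterwards.

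**Formulas.**
- Design effect: DEFF = 1 + (5 − 1) × 0.010 = 1.04.
- Standard error: SE = 5 × √[1.04 × (1/n₁ + 1/n₂)].
- Power: noncentral t with noncentrality 4/SE and n₁ + n₂ − 2 degrees of freedom (participant level), unless stated otherwise.

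**Step 1: counts read as totals, equal arms.**
- 30 participants, 15 per arm: SE = 5 × √(1.04 × 2/15) = 1.862; 4/1.862 = 2.148; power 54.6%, against 85% stated.
- 50 participants, 25 per arm: SE = 5 × √(1.04 × 2/25) = 1.442; 4/1.442 = 2.774; power 77.6%, against 94% stated.

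Neither end is reproduced. The difference detectable with 85% power is 5.8 points with 30 in total and 4.4 points with 50 in total, against the stated 4.

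**Step 2: can another choice rescue the total reading?**

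| Variant | 30 in total | 50 in total |
|---|---|---|
| As stated, equal arms | 54.6% | 77.6% |
| Normal approximation | 57.5% | 79.2% |
| ICC set to 0 | 56.2% | 79.1% |
| One-sided test | 67.4% | 86.2% |
| Unequal split (2 v 4; 4 v 6 libraries) | 49.8% | 75.9% |
| Library-level degrees of freedom (libraries − 2) | 37.7% | 68.2% |

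None reaches the stated range at either end.

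**Step 3: counts read per equal arm.**

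| Libraries per arm | Participants per arm | SE | 4/SE | Power |
|---|---|---|---|---|
| 6 | 30 | 1.317 | 3.038 | 84.8% |
| 7 | 35 | 1.219 | 3.282 | 89.9% |
| 8 | 40 | 1.140 | 3.508 | 93.4% |
| 9 | 45 | 1.075 | 3.721 | 95.7% |
| 10 | 50 | 1.020 | 3.922 | 97.3% |

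The lower end now agrees with 85%. The upper end does not: 94% falls at about 8 libraries and 40 participants per arm (93.4%; 93.9% by the normal approximation). The stated range therefore fits about 60-80 participants in 12-16 libraries. With library-level degrees of freedom the per-arm reading gives 78.2% to 96.0%.

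**Step 4: one arm fixed at 30, the other running from 30 to 50.** At 30 v 50, SE = 5 × √[1.04 × (1/30 + 1/50)] = 1.178 and 4/1.178 = 3.397. The range is 84.8% to 91.8% by the named t-test, or 86.0% to 92.5% by the normal approximation. This comes closer but still falls short of 94%, and the protocol does not describe such a design.

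**Step 5: 125 enrolled.** At 5 per library, 125/5 = 25 libraries. The alternatives of 10 and 6 libraries are assumptions, with DEFF recalculated for the larger clusters (12.5 and 20.8 per library).

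| Libraries | DEFF | Power, participant-level df | Power, library-level df |
|---|---|---|---|
| 25 (60 v 65 participants) | 1.04 | 99.2% | 98.7% |
| 10 (equal arms) | 1 + 11.5 × 0.01 = 1.115 | 98.8% | 95.8% |
| 6 (equal arms) | 1 + 19.83 × 0.01 = 1.198 | 98.2% | 85.7% |

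**The case against.** The strongest reply is that the counts were meant per arm. The agreement at the lower end (84.8% against 85%) supports this as the origin of the calculation. On that reading the plan does not overstate its power: the lower end is right to rounding and the upper end is understated (94% against 97.3%). This stands as a limit on the harm, and the 30-point gap applies only to the total reading. It does not clear the sentence, because the text does not say per arm, and supplying those words still leaves the upper end wrong.

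A second reply is that baseline adjustment, which the Analysis Plan includes through a structural equation model, would add power. It could, but the sentence names a t-test and gives no pre/post correlation. Multiplying the residual SD by √(1 − r²), assumed correlations of 0.3 and 0.5 take the total reading to 58.5%-81.3% and 66.8%-88.1%. An assumed 0.7 gives 82.7%-96.7%. Individual ends can be approached with higher values, but none of these gives 85% to 94%.

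A third is that 125 is an entry in a form field that exceeds both 30-50 and 60-100, so it may simply be a ceiling. That is fair, and 125 contradicts nothing. Nor is 5 per library a fixed rule: it is an average, and the monthly sessions at one library could draw more. The point is only that its role is not stated. The study schema was uploaded separately and is not available here; it might give the number of libraries or the allocation.

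**Conclusion.** The concern holds. With the protocol's own inputs and the test it names, power is 54.6% to 77.6% if the counts are totals and 84.8% to 97.3% if they are per equal arm. Neither reproduces both ends of 85% to 94%. Taken as totals, the claim is too high by about 30 points (85 − 54.6) and 16 points (94 − 77.6). For totals this does not depend on the allocation assumption, since an equal or nearly equal split of whole libraries gives the highest power.

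The consequence is conditional. If recruitment were set at 30-50 in total, the trial would be underpowered for its own 4-point difference. If 125 are enrolled, power at the stated ICC is about 98% to 99% with participant-level degrees of freedom. With library-level degrees of freedom it would be 95.8% in 10 libraries and 85.7% in 6, both being assumed numbers of libraries. The arithmetic is certain. What remains unknown is which size the sponsor intends, and that is why the statement should be corrected.

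**What to change.** In the Analysis Plan, state whether participants and libraries are totals or per arm, give the allocation ratio, and report the power that matches:

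- 30-50 participants in 6-10 libraries in total: 55% to 78%.
- 6-10 libraries per arm, equal arms (60-100 participants in 12-20 libraries): 85% to 97%.
- If 85% to 94% is to stand: about 30-40 participants per arm (60-80 participants in 12-16 libraries).

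These figures use participant-level degrees of freedom, and the text should say which degrees of freedom were used. Then say whether 125 is a target, a ceiling or an allowance for loss. Give the number of libraries and the expected cluster sizes for it, including the library with monthly sessions, and compute the power for that configuration.

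The cost is wording and one recalculation. The stated power may become less favourable, but the correction itself requires no additional participants.

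### The only baseline-adjusted comparison of arms is a structural equation model with no inference method stated; default large-sample inference would put a nominal 5% test at about 5.6% (125 participants) to 8.0% (30 participants)

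*Combined protocol and SAP*

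**What the plan says.** The Analysis Plan section of the combined protocol and SAP has three analyses of the outcome scales.

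- Between arms, unadjusted: "independent t-test will assess differences in pre-test knowledge and attitudes prior to intervention between control and experimental groups, and again with a posttest analysis".
- Within arms: "Paired t-test will assess within cohort changes in knowledge and attitudes".
- Between arms, adjusted: "Structural equation modeling will assess differences in control and treatment participants post scores while adjusting for relevant covariates including baseline knowledge and attitudes".

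The third is the only one that compares arms with allowance for baseline. Two covariates are named; the word *including* leaves the list open. The section does not say whether the model uses observed or latent scores, how it is estimated, or how tests and intervals are formed. No analysis names a library term, although the Design section randomizes whole libraries.

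Two sample sizes appear. The power statement in the Analysis Plan has "Sample sizes of 30-50 participants, when sampling 6-10 libraries, or clusters, with an with an average of 5 subjects in each cluster". The target population section, under "Subjects enrolled by Penn Researchers", gives 125.

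**The concern.** SEM inference is, by default, large-sample inference. Maximum likelihood divides the residual sum of squares by n rather than by the residual degrees of freedom, and the estimate is then referred to a normal distribution. At a few dozen participants both steps make p-values too small and intervals too narrow. With observed scores and complete data, the point estimate for a single outcome is the same as from ANCOVA, so the default would give up exact t inference without a gain in the estimate.

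With few libraries randomized, chance imbalance at baseline is a live possibility, and readers may then look to the adjusted result. If that result comes from an uncorrected default, a false finding in favour of VR (or against it) is somewhat more likely than its nominal level suggests. The plan describes no mediation, measurement or path question that would justify accepting this.

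**Working it through.** **Inputs.** From the Analysis Plan: 30-50 participants, 6-10 libraries, 5 per library, a 4-point difference, SD 5, ICC 0.010, two-sided 0.05, two named covariates. From the target population section: 125 participants. Assumed: observed scores, maximum likelihood, normal reference, independent participants except where stated.

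**1. Which n does 30-50 mean?** The plan's figure is "achieves 85% to 94% power to detect a difference in OOKS scores". The design effect is 1 + (5 - 1) x 0.01 = 1.04, and the standard error of the difference is 5 x sqrt(1.04 x 2 / n per arm). Using the noncentral t with participant degrees of freedom:

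| n per arm | SE | 4 / SE | Power |
|---|---|---|---|
| 15 (30 in total) | 1.862 | 2.148 | 54.6% |
| 25 (50 in total) | 1.442 | 2.774 | 77.6% |
| 30 | 1.317 | 3.038 | 84.8% |
| 40 | 1.140 | 3.508 | 93.4% |
| 50 | 1.020 | 3.922 | 97.3% |

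The stated 85% matches 30 per arm and 94% matches about 40 per arm. Neither reading of 30-50 gives both ends, so I carry three cases: 30-50 in total, 60-100 in total (30-50 per arm), and 125.

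**2. Actual size of the default test.** With k covariates plus intercept and arm, df = n - k - 2. The maximum-likelihood standard error is the least-squares one times sqrt(df / n), so rejecting beyond 1.96 is the same as rejecting when |t| exceeds 1.96 x sqrt(df / n):

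size = 2 x P(t_df > 1.96 x sqrt(df / n)).

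The interval width relative to the correct one is 1.96 x sqrt(df / n) / t(0.975, df).

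Example, n = 30 and k = 2: df = 26; 1.96 x sqrt(26/30) = 1.825; size = 8.0%; width ratio = 1.825 / 2.056 = 0.888.

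| n in total | Size, k = 2 (named) | Width ratio, k = 2 | Size, k = 6 (assumed) | Width ratio, k = 6 |
|---|---|---|---|---|
| 30 | 8.0% | 0.888 | 10.7% | 0.809 |
| 50 | 6.6% | 0.934 | 8.0% | 0.890 |
| 60 | 6.3% | 0.945 | 7.4% | 0.909 |
| 100 | 5.8% | 0.967 | 6.3% | 0.947 |
| 125 | 5.6% | 0.974 | 6.0% | 0.9575 |

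A simulation with independent participants (20,000 replicates) agrees: for k = 2, 8.1% at 30, 6.5% at 50 and 5.6% at 125. A likelihood-ratio test does not remove the excess: for k = 2, 7.1% at 30, about 6.2% at 50 and 5.4% at 125.

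**3. Adding library.** Simulating the plan's ICC of 0.010 with 5 per library and ignoring it in the model, the default test with k = 2 has size 8.6% at 30, 7.4% at 50 and 6.3% at 125. An ordinary t-based ANCOVA with participant degrees of freedom also drifts, to 5.3%-5.7% across the cases run. The 125 case used 25 libraries of 5. Spread over 6-10 libraries, 125 would mean 125/10 = 12.5 to 125/6 = 20.8 per library, and clustering would matter more.

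**4. Reference distribution once library is the unit.** With 6-10 libraries, a test that should use libraries minus 2 degrees of freedom but uses a normal reference has size 2 x P(t_4 > 1.96) = 12.2% at 6 libraries and 2 x P(t_8 > 1.96) = 8.6% at 10.

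**The case against.** The strongest reply is that the excess is assumed rather than read. The plan does not say that uncorrected maximum likelihood with a normal reference will be used; bootstrap or small-sample-corrected inference would fit its wording equally well. That stands, and it is why every figure here is conditional. It does not dispose of the point, since a plan that is silent leaves the default open.

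A reader might infer that the adjusted test will run at up to 10.7%. The documents do not support that. It needs n = 30 in total and four covariates beyond the two named. At the enrolment of 125, the excess is about one percentage point or less.

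A reader might also infer that the SEM carries the trial's conclusion at a stated 5% level. No analysis is designated primary, and the 0.05, the 4-point difference and the power all belong to a t-test. An unadjusted posttest t-test between arms is also planned, and it already uses a t reference.

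Nor can one say that SEM could add nothing. It might model both scales jointly or retain incomplete pre-post pairs. The plan claims neither purpose. I have no calculation for a latent-variable version and make no claim about its size.

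Finally, clustering is the larger problem with so few libraries, and participant-level ANCOVA alone would not give correct intervals. That is right, and the replacement has to handle library.

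**Conclusion.** The point holds as a specification gap with a modest, conditional effect on error rates. SEM is the only baseline-adjusted comparison of arms, its inference is unspecified, and nothing in the plan requires it.

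Under the usual default, on observed scores with the two named covariates and independent participants, the direction is anti-conservative at every sample size the plan could mean. Size is 6.6%-8.0% at 30-50 in total, 5.8%-6.3% at 60-100, and 5.6% at 125; intervals are 7%-11%, 3%-5% and 3% too narrow. Six covariates, an assumption, would raise the sizes to 8.0%-10.7%, 6.3%-7.4% and 6.0%. Ignoring library adds to all of these.

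If 125 is confirmed as the analysed number and library is handled properly, the part of the excess due to SEM alone is small.

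**What to change.** Replace the SEM sentence with:

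> For each scale, the adjusted VR-control difference in posttest score will be estimated by a linear (ANCOVA) model on observed total scores, with arm and the pretest score of the same scale, with library accounted for (e.g. a random library intercept fitted by REML), and t-based tests and 95% confidence intervals using small-sample degrees of freedom that reflect the number of libraries.

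Name the degrees-of-freedom rule in advance (libraries minus 2 is the simple choice), so that an estimated library variance of zero does not return the test to participant-level degrees of freedom. Further covariates, such as the pretest score of the other scale, should be few and listed beforehand. Label any SEM exploratory and state its estimator and standard-error method. Reconcile the 30-50 of the power statement with the 125 under enrolment, and say whether 30-50 is in total or per arm.

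No new data are needed. The cost is wider intervals: with libraries minus 2 degrees of freedom the multiplier rises from 1.96 to 2.78 at 6 libraries (2.78 / 1.96 = 1.42) and to 2.31 at 10 (2.31 / 1.96 = 1.18). The sample-size statement should be reworked on the same basis.
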